Determination of ORR will be assessed by the Investigator according to the MDS International Working Group (IWG) criteria (Cheson 2006, Table 9 and Table 10).

Upon disease progression, all subjects in the study will be followed approximately every 12 weeks for survival and the use of subsequent therapy until either death or 12 months after accrual of the study has been completed, whichever occurs first. Information on survival and subsequent anticancer therapy may be collected by phone.

Subjects who terminate treatment for reasons other than death or disease progression will be assessed at regular intervals for disease progression (approximately every 12 weeks) and leukemic transformation (monthly blood counts). Disease assessments performed during the first 9 months from the start of the subject's participation in the study will include bone marrow evaluation. Thereafter, bone marrow evaluations will occur during disease assessments in accordance with institutional standard practice. These assessments will continue until disease progression, withdrawal of subject's consent to study procedures or initiation of another anticancer therapy.

All subjects will be followed-up for safety during treatment and up to approximately 30 days (30 \pm 7 days) after treatment discontinuation or until immediately before the initiation of another anticancer therapy, whichever occurs first. Additional follow up may be implemented until the subject recovers from any emergent treatment related toxicity or the adverse event is considered irreversible by the Investigator. Target organ toxicities will be monitored via clinical and laboratory assessments using the National Cancer Institute Common Terminology Criteria for Adverse Events version 4.03 (NCI CTCAE v 4.03) criteria.

NUMBER OF SUBJECTS PLANNED: Approximately 36 eligible study subjects.

SUBJECT SELECTION:

Inclusion Criteria

For inclusion of a subject in the study, all of the following inclusion criteria must be fulfilled:

- 1. Subject is at least 18 years of age.
- 2. Documented pathological evidence of MDS as defined by the World Health Organization (WHO) criteria (Table 8).

- 3. Eastern Cooperative Oncology Group (ECOG) performance status 0, 1 or 2.
- 4. Subjects have no known curative treatment.
- 5. Subject is willing and able to comply with scheduled visits, treatment plans, laboratory tests and other procedures (including bone marrow assessments).

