 initiation of any other anticancer therapy.
- 4. Follow up visit required only for subjects who terminated treatment for reasons other than death or disease progression.
- 5. Information on subject's survival and use of subsequent anticancer therapy may be collected by phone. Upon disease progression, all subjects will be followed approximately every 12 weeks for survival and the use of subsequent therapy until either death or 12 months after accrual in the subject's study cohort has been completed, whichever occurs first.
- Medical history is to include demographics, primary diagnosis and WHO classification, outcome and duration of response to prior cancer therapy and any ongoing AEs
- 7. At the screening visit, record the number of RBC, whole blood and platelet transfusions for the four months prior to Cycle 1 Day 1; for all other visits, the number of transfusions should be recorded since the last study visit.
- Assessed from date of first signature of ICF, throughout the course of treatment and approximately 30 days after treatment discontinuation. Additional assessments may be performed until AE resolution or the AE is deemed irreversible by the Investigator.
- 9. Assessment is to be performed within 14 days prior to the first administration of study drug.
- If not collected within the 14 days prior to Cycle 1 Day 1, record subject's weight and vital signs prior to dosing on Cycle 1
 Day 1 only.
- 11. Assessment is to be performed within 72 hours prior to first administration of study drug on Day 1 of Cycle 1.
- 12. To be performed in women with childbearing potential only
- 13. Assessment is to be performed beginning on Cycle 2 Day 1 and Day 1 of every cycle thereafter.
- 14. Fasting for laboratory testing is not required. Laboratory tests may be conducted on additional time points if deemed necessary by the Investigator. Samples will be analyzed locally at the clinical site or its reference laboratory. Laboratory assessments may be repeated if values are borderline to inclusion level or may change due to best supportive care measures. Hematology should include: hemoglobin, reticulocytes, platelets, WBCs, neutrophils, neutrophil precursors (promyelocytes, myelocytes, metamyelocytes, band neutrophils), monocytes, lymphocytes and blasts. Serum chemistry should include: AST, ALT, total bilirubin, creatinine, BUN, potassium and calcium. Coagulation should include: PT/INR, APTT.

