Hematologic assessments, including peripheral blood evaluations and review of transfusion requirements, will be performed at screening and at least monthly until disease progression. Disease assessments will also be performed at screening and at least once every approximately 12 weeks starting at the end of cycle 3. As part of the disease assessment at screening and during Cycles 3, 6 and 9, bone marrow evaluation will be performed. Thereafter, bone marrow evaluations will occur during disease assessments in accordance with institutional standard practice. Additional hematologic or disease assessments may be conducted if deemed necessary by the Investigator. The timing of the hematologic and disease assessments should be maintained as much as possible independently of potential treatment cycle delays.

Determination of ORR will be assessed by the Investigator according to the MDS IWG criteria (Table 9 and Table 10).

Upon disease progression, all subjects in the study cohort will be followed approximately every 12 weeks for survival and the use of subsequent therapy until either death or 12 months after accrual of the study cohort has been completed, whichever occurs first. Information on survival and subsequent anticancer therapy may be collected by phone.

Subjects who terminate treatment for reasons other than death or disease progression will be assessed at regular intervals for disease progression (approximately every 12 weeks) and leukemic transformation (monthly blood counts). Disease assessments performed during the first 9 months from the start of the subject's participation in the study will include bone marrow evaluation. Thereafter, bone marrow evaluations will occur during disease assessments in accordance with institutional standard practice. These assessments will continue until disease progression, withdrawal of subject's consent to study procedures or initiation of another anticancer therapy.

All subjects will be followed-up for safety during treatment and up to approximately 30 days (30 \pm 7 days) after treatment discontinuation or until immediately before the initiation of another anticancer therapy, whichever occurs first. Additional follow up may be implemented until the subject recovers from any emergent treatment related toxicity or the adverse event is considered irreversible by the Investigator. Target organ toxicities will be monitored via clinical and laboratory assessments using the NCI CTCAE v.4.03 criteria.

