9.12 Non-permitted Treatments

Use of the following medications and therapies is not allowed during the study:

- Investigational agents other than tipifarnib.
- Any other anticancer therapy, including radiation or surgery, for the primary disease under study.
- Anti-apoptotic agents (e.g. amifostine) or immunosuppressive drugs (e.g. cyclosporine A, ATG).
- Corticosteroids > 10 mg prednisone daily or its equivalent
- Subjects should not use enzyme-inducing anti-convulsants (e.g. phenytoin, phenobarbital, and carbamazepine) while taking tipifarnib. If needed, subjects may use non-enzyme-inducing anti-convulsants (e.g. gabapentin, topiramate, valproate) while taking tipifarnib.

If the administration of a non-permitted concomitant drug becomes necessary during the study, e.g. because of AEs or disease progression, the subject in question will be withdrawn from the study, and the subject's data obtained before the withdrawal may be used for safety and efficacy evaluations.

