10.1 Efficacy Variables

Hematologic assessments, including peripheral blood evaluations and review of transfusion requirements, will be performed at screening and at least monthly until disease progression. Disease assessments will also be performed at screening and at least once every approximately 12 weeks starting at the end of cycle 3. As part of the disease assessment at screening and during Cycles 3, 6 and 9, bone marrow evaluation will be performed. Thereafter, bone marrow evaluations will occur during disease assessments in accordance with institutional standard practice. Additional hematologic or disease assessments may be conducted if deemed necessary by the Investigator.

Disease response assessment will be performed by the Investigator according to the MDS IWG criteria (Table 9 and Table 10).

Determination of RBC TI (secondary endpoint) will be assessed by the investigator through the review of subject transfusion requirements and hemoglobin levels. RBC TI will be defined as the absence of the intravenous infusion of any RBC transfusion during any consecutive "rolling" 56 days during the treatment period, i.e. days 1 to 56, days 2 to 57, days 3 to 58, etc. and $a \ge 1$ g/dL increase in hemoglobin level.

Upon disease progression, all subjects in the study cohort will be followed approximately every 12 weeks for survival and the use of subsequent therapy until either death or 12 months after accrual of the study cohort has been completed, whichever occurs first. Information on survival and subsequent anticancer therapy may be collected by phone.

Subjects who terminate treatment for reasons other than death or disease progression will be assessed at regular intervals for disease progression (approximately every 12 weeks) and leukemic transformation (monthly blood counts). Disease assessments performed during the first 9 months from the start of the subject's participation in the study will include bone marrow evaluation. Thereafter, bone marrow evaluations will occur during disease assessments in accordance with institutional standard practice. These assessments will continue until disease progression, withdrawal of subject's consent to study procedures or initiation of another anticancer therapy.

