11.6 Post Treatment Follow up

11.6.1 Subjects who Terminate Treatment for Reasons other than Death or Disease Progression

Subjects who terminated treatment for reasons other than death or disease progression will be assessed at regular intervals for disease progression and leukemic transformation.

The assessments to be conducted at each monthly visit are:

• Perform hematology tests (hemoglobin, platelets, WBCs, neutrophils, neutrophil precursors, monocytes, lymphocytes and blasts)

The assessments to be conducted at each approximately every 12 weeks visit are

- Record any RBC, whole blood and platelet transfusions that were received since the last study visit.
- Perform disease and response assessment:

- Perform bone marrow aspirate as part of the assessments if post-treatment follow-up visit is conducted during the first 9 months from the start of the subject's participation in the study. Thereafter, bone marrow evaluations will occur during post-treatment follow-up visits in accordance with institutional standard practice. If the bone marrow aspirate is inadequate, a bone marrow biopsy should be performed. If on this bone marrow sample, a CR or PR is observed, a bone marrow aspirate with cytogenetic assessment must be repeated 1 month later.
- o Investigator review of subject RBC transfusions, hematology and bone marrow evaluation (if available) for completion of response assessment.
- Assessments of AEs and concomitant medications may also be conducted if AEs were not resolved at the time of the End of Treatment visit.

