Subjects who received a starting dose of 900 mg bid during the conduct of the original version of this protocol may be dose reduced to the 600 mg bid dose at the discretion of the investigator (protocol Amendment 1). Subjects who received tipifarnib on Days 1 – 7 and Days 15 – 21 during the conduct of the original version and amendment 1 of this protocol, may transition to

the new treatment administration schedule (tipifarnib on Days 1-7 in 28 day cycles) beginning on Day 1 of their next cycle.

Subjects accrued prior to Protocol Amendment 3, 09 July 2017, will not be included in the total disposition and were not considered in the sample size determination detailed in section 5 of this SAP. The estimated number of 36 subjects enrolled do not include these subjects. For analysis, this subject population will only be included in the Total Adverse Event tables.

In the absence of unmanageable toxicities, subjects may continue to receive tipifarnib treatment until disease progression. If a complete response (CR) is observed, therapy with tipifarnib will be maintained for at least 6 months beyond the start of response.

Hematologic assessments, including peripheral blood evaluations and review of transfusion requirements, will be performed at screening and at least monthly until disease progression. Disease assessments will also be performed at screening and at least once every approximately 12 weeks starting at the end of cycle 3. As part of the disease assessment at screening and during Cycles 3, 6 and 9, bone marrow evaluation will be performed. Thereafter, bone marrow evaluations will occur during disease assessments in accordance with institutional standard practice. Additional hematologic or disease assessments may be conducted if deemed necessary by the Investigator. The timing of the hematologic and disease assessments should be maintained as much as possible independently of potential treatment cycle delays.

Determination of ORR will be assessed by the Investigator according to the MDS International Working Group (IWG) criteria (Table 8 and Table 9 in the study protocol).

Upon disease progression, all subjects in the study will be followed approximately every 12 weeks for survival and the use of subsequent therapy until either death or 12 months after accrual of the study has been completed, whichever occurs first. Information on survival and subsequent anticancer therapy may be collected by phone.

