Subjects who terminate treatment for reasons other than death or disease progression will be assessed at regular intervals for disease progression (approximately every 12 weeks) and leukemic transformation (monthly blood counts). Disease assessments performed during the first 9 months from the start of the subject's participation in the study will include bone marrow evaluation. Thereafter, bone marrow evaluations will occur during disease assessments in accordance with institutional standard practice. These assessments will continue until disease progression, withdrawal of subject's consent to study procedures or initiation of another anticancer therapy.

All subjects will be followed-up for safety during treatment and up to approximately 30 days (30 ± 7 days) after treatment discontinuation or until immediately before the initiation of another anticancer therapy, whichever occurs first. Additional follow up may be implemented until the subject recovers from any emergent treatment related toxicity or the adverse event is considered

irreversible by the Investigator. Target organ toxicities will be monitored via clinical and laboratory assessments using the NCI CTCAE v. 4.03 criteria.

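### Survival contact starts only at progression, so deaths after a pre-progression therapy switch or a withdrawal from procedures can be missed in 1-year survival; separately, duration of response leaves some deaths unclassified

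*Protocol*

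**What the plan says.** **Survival contact.** The synopsis states: "Upon disease progression, all subjects in the study will be followed approximately every 12 weeks for survival and the use of subsequent therapy". Table 1 note 5 has the same trigger: "Upon disease progression, all subjects will be followed approximately every 12 weeks for survival". Protocol 8.1 and 10.1 apply it to the cohort: "Upon disease progression, all subjects in the study cohort will be followed approximately every 12 weeks for survival and the use of subsequent therapy". Protocol 11.6.2, SAP 4.1 ("Upon disease progression, all subjects in the study will be followed approximately every 12 weeks for survival") and note 5 of the SAP schedule (SAP 4.6) agree. No passage starts survival contact at any other event.

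**Subjects off treatment without progression.** Under Protocol 11.6.1 they "will be assessed at regular intervals for disease progression and leukemic transformation". The section lists monthly blood counts and, about every 12 weeks, transfusion records and a disease assessment. It lists no survival or subsequent-therapy contact. Protocol 8.1 says when this follow-up ends: "These assessments will continue until disease progression, withdrawal of subject's consent to study procedures or initiation of another anticancer therapy". SAP 4.1 repeats the stopping points: "withdrawal of subject's consent to study procedures or initiation of another anticancer therapy". Safety follow-up lasts about 30 days after the last dose and also ends at a new anticancer therapy (Protocol 8.1, 10.9). Optional further follow-up covers only unresolved treatment-related toxicity. Where a non-permitted drug is needed, Protocol 9.12 says "the subject in question will be withdrawn from the study, and the subject's data obtained before the withdrawal may be used"; other anticancer therapy is on that section's list.

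**Endpoints.** One-year survival, one-year PFS and duration of response (DOR) are secondary objectives (Protocol 6.2). Survival and PFS count death from any cause, with no exception for subjects who switched (Protocol 12.2.1, SAP 9.2). DOR names documented progression as its only event and lists three censoring conditions.

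**The concern.** An endpoint that counts every death needs vital status on every subject, whatever ended treatment. Here, collection depends on progression having been documented. A subject who switches therapy before progressing leaves the pre-progression schedule without entering the post-progression one. The same holds for a subject who withdraws from study procedures but not from data collection. Deaths after that point have no planned route into the database and may not be recoverable at analysis.

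SAP 7.5 would censor such subjects. That is unbiased only if their prognosis is unchanged after they leave; otherwise the 1-year estimate is off. If prognosis is unchanged, only precision is lost.

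The DOR wording raises a smaller, separate problem: two analysts following the same text could classify the same death differently.

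**Working it through.** **1. The plan's own figures.** The documents give no number for survival follow-up or DOR. Their design figures concern response only. With 11 then 18 subjects, continuing at 2 or more responses and succeeding at 4 or more, the probability of success is the sum over x1 = 2 to 11 of P(X1 = x1) × P(X2 ≥ 4 − x1). It is 0.0875 at a 10% rate (stated 0.087) and 0.8001 at 30% (stated 80%). The stage 1 stopping probabilities are 0.697 and 0.113, as stated. None of these depends on survival or DOR data.

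**2. Who has planned survival ascertainment.**

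| Subject's path | Planned route to a death |
|---|---|
| On treatment | Study visits and safety reporting |
| Progressed | 12-weekly survival contact |
| Off treatment, not progressed, no switch or withdrawal | Monthly blood counts and 12-weekly visits |
| Off treatment, then new therapy before progression | None after the switch |
| Withdrew from procedures before progression, data permission intact | Safety window only |
| Permission to use health information withdrawn | None, properly (Protocol 8.4) |

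The fourth and fifth rows are the gap.

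**3. Bounds without a survival model.** Each subject with unknown 1-year status widens the best/worst-case range by 1/18 = 5.6 points in a cohort of 18. Four such subjects widen it by 4/18 = 22.2 points.

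**4. Illustration of bias; every input is assumed.** The documents give no switching rate and name no estimator for 1-year survival; Kaplan-Meier is named only for DOR. Take 50% one-year survival before any switch, so λ = −ln(0.5) = 0.693 per year. Let p be the share who would switch within the year in the absence of death, k = −ln(1 − p), s = λ + k, and h the hazard ratio after the switch. Then

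true S(1) = exp(−s) + ∫₀¹ k·exp(−s·u)·exp(−hλ(1−u)) du,

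while Kaplan-Meier censored at the switch targets exp(−λ) = 0.500. For example, p = 0.30 and h = 3 give 0.350 + 0.078 = 0.428, an error of 0.500 − 0.428 = +7.2 points.

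| p | h = 0.5 | h = 1 | h = 2 | h = 3 | Error, reported minus true (points) |
|---|---|---|---|---|---|
| 0.10 | 0.510 | 0.500 | 0.486 | 0.477 | −1.0 to +2.3 |
| 0.30 | 0.531 | 0.500 | 0.456 | 0.428 | −3.1 to +7.2 |

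The share actually seen to switch is (k/s)(1 − exp(−s)): 7.3% and 22.1%, or about 1.3 and 4.0 of 18 subjects.

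As a cross-check, the earlier phase 2 study's median survival of 11.7 months (Protocol 5.5.3) gives exp(−ln2 × 12/11.7) = 49.1% at one year if survival is exponential. Simulation from that base, with 10-30% marked to leave at a uniform time in months 1-9 and the hazard then 1 to 3 times as high, gives an overstatement of 0 to about 8 points.

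**5. Against sampling error.** For 9 of 18 alive, the exact 95% interval is 26% to 74%.

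**6. DOR rules for a responder with no new therapy** (Protocol 12.2.1, SAP 9.2).

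| Outcome | Classification |
|---|---|
| Documented progression, at most 1 missed visit | Event |
| Death or progression after more than 1 missed visit | Censored (condition 2) |
| Alive without progression at cutoff | Censored (condition 3) |
| Death without progression after 0 or 1 missed visits | Not stated |

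Condition 2 implies that an earlier death is an event, but the definition does not say so. If the missed-visit phrase applies to progression only, every death is censored. At a 30% response rate a cohort has 0.3 × 18 = 5.4 responders. Suppose five responses end at 2, 4, 6, 8 and 10 months and one of those ends is a death. The median is 6 months if the death is an event. If it is censored, the median is 8 when it is the second or third end, 6 when it is the fourth or fifth, and 6 or 7 by convention when it is the first.

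**The case against.** The best defence is proportion. These are secondary endpoints in small cohorts. Protocol 5.4 describes limited therapeutic options, so switching may be uncommon. SAP 7.5 already says that dropouts without confirming events are censored in survival analysis. With an unchanged hazard, the Kaplan-Meier bias is zero. All of this stands and limits the size of the point. It does not close the gap: SAP 7.5 is an analysis rule and cannot recover an uncollected death, and SAP 8.6 lists survival dates without creating a step that collects them.

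Five stronger readings are tempting, and the documents do not support them:

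- *Everyone who stops before progression is lost for survival.* Those who neither switch nor withdraw are seen monthly, and deaths on treatment or in the safety window can be captured.
- *Reported survival will be too high.* The direction depends on prognosis after the switch, which the documents do not give.
- *Reduced denominators add a further bias.* That is SAP 7.5's general sentence on missing data. Its next sentence deals with survival analysis and specifies censoring, and survival is defined as a time.
- *More phone contact also repairs PFS.* Progression assessments still stop at the switch. A death counted later, with any intervening progression unassessed, could place the PFS event too late.
- *DOR must be redefined to include death.* A progression-only definition is legitimate, and a subject without the named event would ordinarily be censored. However, condition 2 points the other way, and SAP 7.5 speaks of dropouts, not deaths.

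**Conclusion.** The survival gap holds on the text, within a narrow group: subjects who switch therapy before progression, and those who withdraw from procedures without withdrawing permission to collect health information. Their later deaths can be missed in 1-year survival. Size and direction are unknown. Under the assumed 50% survival, 10-30% switching and hazard ratio 0.5-3, the Kaplan-Meier error is about −3 to +7 points, smaller than the sampling error at n=18. Withdrawals were not modelled in that calculation. The stage 1 and final response-rate decisions are unaffected. The change is worth making because it is cheap and a missed death may not be recoverable later.

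The DOR ambiguity is also real but smaller and separate. The response criteria tables (Protocol Tables 9 and 10) are not in the text available, so whether they address death could not be checked.

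**What to change.** 1. **Survival contact.** In the synopsis, Table 1 note 5, Protocol 8.1, 10.1, 11.6.1 and 11.6.2, SAP 4.1 and SAP schedule note 5, start the existing 12-weekly phone contact for survival and subsequent therapy when treatment ends for any reason. Existing follow-up visits serve as the contact while they continue. The exception is withdrawal of permission to collect health information.
2. **Protocol 9.12.** Reconcile its withdrawal wording with this contact.
3. **PFS.** State in SAP 9.2 how PFS handles new anticancer therapy before a later death is counted as a PFS event.
4. **DOR.** In Protocol 12.2.1 and SAP 9.2, state one rule for death without progression: either count it as an event after 0 or 1 missed visits, as PFS does and condition 2 implies, or censor every such death.

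**Cost.** Text edits at eleven places (eight protocol, three SAP) and a protocol amendment with IRB/IEC approval (Protocol 12.5, 14.5). The consent form should be checked for later contact; those pages were not available. The extra calls cover about 1 to 4 switchers per cohort of 18 under the assumed rates, plus any withdrawals, which were not counted. Counting deaths as DOR events may shorten the reported duration. Sample size, significance level and power do not change.
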